13.1 Regulatory and ethical compliance

This clinical study was designed and shall be implemented, executed and reported in accordance with the ICH Harmonized Tripartite Guidelines for Good Clinical Practice, with applicable local regulations (including European Directive 2001/20/EC, US CFR 21), and with the ethical principles laid down in the Declaration of Helsinki.

13.2 Responsibilities of the investigator and IRB/IEC

Before initiating a trial, the investigator/institution must obtain approval/favorable opinion from the Institutional Review Board/Independent Ethics Committee (IRB/IEC) for the trial protocol, written informed consent form, consent form updates, participant recruitment procedures (e.g., advertisements) and any other written information to be provided to participants. Prior to study start, the investigator is required to sign a protocol signature page confirming his/her agreement to conduct the study in accordance with these documents and all of the instructions and procedures found in this protocol and to give access to all relevant data and records to Novartis monitors, auditors, Novartis Quality Assurance representatives, designated agents of Novartis, IRBs/IECs, and regulatory authorities as required. If an inspection of the clinical site is requested by a regulatory authority, the investigator must inform Novartis immediately that this request has been made.

13.3 Publication of study protocol and results

The protocol will be registered in a publicly accessible database such as clinicaltrials.gov and as required in EudraCT. In addition, after study completion (defined as last patient last visit) and finalization of the study report the results of this trial will be submitted for publication and posted in a publicly accessible database of clinical trial results, such as the Novartis clinical trial results website and all required Health Authority websites (e.g. Clinicaltrials.gov, EudraCT etc.).

For details on the Novartis publication policy including authorship criteria, please refer to the Novartis publication policy training materials that were provided to you at the trial investigator meetings.

13.4 Quality Control and Quality Assurance

Novartis maintains a robust Quality Management System (QMS) that includes all activities involved in quality assurance and quality control, to ensure compliance with written Standard Operating Procedures as well as applicable global/local GCP regulations and ICH Guidelines.

Audits of investigator sites, vendors, and Novartis systems are performed by auditors, independent from those involved in conducting, monitoring or performing quality control of the clinical trial. The clinical audit process uses a knowledge/risk based approach.

Audits are conducted to assess GCP compliance with global and local regulatory requirements, protocols and internal SOPs, and are performed according to written Novartis processes.

14 Protocol adherence

This protocol defines the study objectives, the study procedures and the data to be collected on study participants. Additional assessments required to ensure safety of participants should be administered as deemed necessary on a case by case basis. Under no circumstances including incidental collection is an investigator allowed to collect additional data or conduct any additional procedures for any purpose involving any investigational drugs under the protocol, other than the purpose of the study. If despite this interdiction prohibition, data, information, observation would be incidentally collected, the investigator shall immediately disclose it to

Novartis and not use it for any purpose other than the study, except for the appropriate monitoring on study participants.

Investigators ascertain they will apply due diligence to avoid protocol deviations. If an investigator feels a protocol deviation would improve the conduct of the study this must be considered a protocol amendment, and unless such an amendment is agreed upon by Novartis and approved by the IRB/IEC and Health Authorities, where required, it cannot be implemented.

## Document History – Changes compared to previous final version of SAP

Date	Time point	Reason for update	Outcome for update	Section and title impacted (Current)
12-APR-2021	Prior to FPFV	Creation of 1 st draft version (0.1)	For Sponsor review	NA
20-APR-2021	Prior to FPFV	Creation of 2 nd draft version (0.2)	After Sponsor review	NA
29-APR-2021	Prior to first patient first vaccination	First final version	Finalization	NA
09-FEB-2022	After data review for 2 nd interim analysis	CSP Amendment Data Review	Analyses of FACS data (CD4+ and CD8+ cell etc) added Subgroup analysis for patients with/without booster vaccination added	
26-SEP-2026	After final data review	Modification of Efficacy Analysis Set	To avoid that patients with non-missing secondary efficacy parameters are excluded from efficacy analysis set	

## List of abbreviations

AE	Adverse event
ATC	Anatomical Therapeutic Classification
CI	Confidence interval
CSP	Clinical Study Protocol
CSR	Clinical Study Report
CV	Coefficient of variation
eCRF	Electronic Case Report Form
DMT	Disease modifying therapy
MedDRA	Medical Dictionary for Drug Regulatory Affairs
MS	Multiple sclerosis
RAP	Report and Analysis Process
SAP	Statistical Analysis Plan
SOC	System Organ Class
SmPC	Summary of Product Characteristics
TFLs	Tables, Figures, Listings
WHO	World Health Organization

## 1 Introduction

This Statistical Analysis Plan (SAP) describes how the statistical analyses of this study will be implemented. Based on the tables/listings/figures (TFL) of resulting from this SAP the Clinical Study Report (CSR) will be written. The TFLs will be attached in section 14 of the CSR.

In addition this SAP describes which patient Data Listings to be attached in section 16.2.1 of the CSR will be generated.

This SAP is not used for other analyses or studies.

It is based on the Study Protocol (CSP), version 02, dated 25th Sep 2021 (2nd Amendment)

### 1.1 Study design

This is a three-cohort, multicenter, open-label, prospective study of 60 patients suffering from multiple sclerosis (MS) currently treated with siponimod or a first-line disease modifying drug (DMT) or without MS treatment planning to undergo a SARS-CoV-2 modRNA vaccination as part of clinical routine and according to the respective SmPC.

MS treatments as part of clinical routine:

- Cohort 1: Siponimod treatment according to EU SmPC without interrupting daily dosing for the purpose of vaccination with SARS-CoV-2 modRNA
- Cohort 2: Siponimod treatment according to EU SmPC interrupting daily dosing for the purpose of vaccination with SARS-CoV-2 modRNA
- Cohort 3: Dimethylfumarate, glatirameracetate, interferon, teriflunomode as per respective EU SmPC or no current treatment with diagnosis of SPMS or with RRMS at risk to develop SPMS (at the discretion of the treating physician)

An interim analysis is planned after all participants have completed the study at one week after the end of the SARS-CoV-2 vaccination cycle in the study. The week +1 data regarding antibody and T-cell response (along with relevant safety data) will be examined as a preliminary evaluation of proof of concept and are the basis for the primary endpoint of the study.

The primary analysis time point is when all participants have completed the study visit 6 months after the end of the SARS-CoV-2 vaccination cycle in the study.

A follow-up analysis is planned after all participants have completed the follow-up visit 12 months.

### 1.2 Study objectives and endpoints

Objective(s)	Endpoint(s)
Primary Objective(s) 

• To estimate the proportion of those achieving seroconversion (i.e. having SARS-CoV-2 serum functional antibodies) after receiving a modRNA

	Endpoint(s) for primary objective(s) 
Proportion of participants achieving seroconversion as defined by detection of SARS-CoV-2 serum functional antibodies one week after second dose of vaccine in participants treated

vaccine in participants treated concomitantly with siponimod and siponimod treatment break.

concomitantly with siponimod and siponimod treatment break (yes/no)

### **Secondary Objective(s)**

- Describing SARS-CoV-2 serum functional antibody levels in participants treated concomitantly with siponimod versus siponimod treatment break versus first-line DMTs and in patients currently not on a DMT
- Describing the T-cell response to modRNA vaccines in participants treated concomitantly with siponimod versus siponimod treatment break versus first-line DMTs and in patients currently not on a DMT
- Describing safety, incl. AEs related to discontinuation and new onset of siponimod treatment and patients developing COVID-19

### **Endpoint(s) for secondary objective(s)**

- SARS-CoV-2 serum functional antibody levels one week, one month and six months after second dose of vaccine in participants treated concomitantly with siponimod versus siponimod treatment break versus first-line DMTs and in patients currently not on a DMT
- SARS-CoV-2 specific T-cell levels one week, one month and six months after second dose of vaccine in participants treated concomitantly with siponimod versus siponimod treatment break versus first-line DMTs and in patients currently not on a DMT measured by e.g. enzyme-linked immunosorbent spot (ELIspot) assay from peripheral blood mononuclear cells that were stimulated with SARS-CoV-2 peptide mix
- AEs, SAEs, incl. patients with clinical confirmed COVID-19, events leading to discontinuation in participants treated concomitantly with siponimod versus siponimod treatment break versus first-line DMTs and in patients currently not on a DMT.

## **2 Statistical methods**

### **2.1 Data analysis general information**

Data analysis will be performed by the CRO [REDACTED]. The software SAS, version 9.2 or higher is used.

According to the small sample size of this study, percentages are presented without decimal places, i.e. as integers without digits.

#### **2.1.1 General definitions**

##### **Study treatments**

The modRNA vaccine and the treatment for MS are defined both as study treatments. More specifically, the MS treatment is established as study treatment from the time of informed consent.

## **Screening failure**

A screening failure is a patient not eligible for the study. Screening failures are identified by:

- any inclusion criterion is violated or

- Any exclusion criterion applies or
- Patient was not vaccinated with a mRNA-vaccine or different mRNA-vaccines.

## **2.2 Analysis sets**

For all analysis sets, participants will be analyzed according to the study treatment(s) received.

The safety analysis set (SAF) will include all participants that received any study drug.

The efficacy analysis set will include all participants who have a valid primary endpoint (i. e. determination of functional antibodies to SARS-CoV-2 at Visit 2 / Week 1) plus those who failed to receive their second dose of vaccine for whatever reason.

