9.1 Discontinuation and completion

9.1.1 Study treatment discontinuation and study discontinuation

All medication is part of clinical routine.

Discontinuation of study treatment for a participant occurs when study treatment is stopped earlier than the protocol planned duration and can be initiated by either the participant or the investigator.

The investigator must discontinue study treatment for a given participant if, he/she believes that continuation would negatively impact the participant's well-being.

Study treatment must be discontinued under the following circumstances:

- Participant/guardian decision
- Pregnancy
- Use of prohibited treatment as per recommendations in the prohibited treatment section
- New medical condition not allowing for continuation of study treatment
- Any situation in which study participation might result in a safety risk to the participant
- Adverse events, abnormal laboratory values or abnormal test result that indicate a safety risk to the participant.

Study discontinuation of a participants occurs under the following circumstances:

- Significant non-compliance
- Retroactive failure to fulfil inclusion/exclusion criteria
- Enrolment in any other clinical trial involving an investigational product or enrolment in any other type of medical research judged not to be scientifically or medically compatible with this study

Participants who decide they do not wish to participate in the study further should NOT be considered withdrawn from the study UNLESS they withdraw their consent (see Section 9.1.2 'Withdrawal of Informed Consent' section). **Where possible, they should return for the assessments indicated** in the Assessment Schedule. If they fail to return for these assessments for unknown reasons, every effort (e.g. telephone, e-mail, letter) should be made to contact the participant/pre-designated contact as specified in the lost to follow-up section. This contact should preferably be done according to the study visit schedule.

Patients completing the vaccination cycle but do not come to the center for the blood draw one week later (6-10 days after second vaccination) will be excluded from the study.

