12.1 Analysis sets

For all analysis sets, participants will be analyzed according to the study treatment(s) received. The safety analysis set will include all participants that received any study drug.

The efficacy analysis sets at one week, one month and six month and additionally after a potential booster vaccination respectively will include all participants who have a valid determination of functional antibodies to SARS-CoV-2 at that time point plus those who failed to receive their second dose of vaccine for whatever reason. The latter will be counted as non-responders. Patients completing vaccination but fail to provide a blood sample at one week after the second vaccination will be excluded from the study and analysis.

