### **2.3.1 Patient disposition**

Patient disposition displays the absolute and relative frequency of screening failures, the number of patients included in the different analysis sets.

The reasons for screening failure, for missed study visits, for exclusion from analysis populations and for prematurely drop-out are described by frequency tables as well as protocol deviations.

The duration of intervals between study visits are displayed by sample statistics. The interval from screening to first vaccination is analyzed by a frequency table for  $\leq 30$  days versus  $> 30$  days.

---

Not applicable, because all patients received their second dose of study vaccine

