## 2.7 Analysis of secondary efficacy objective(s)

### 2.7.1 Secondary endpoints

The secondary endpoints are analyzed descriptively within each cohort. The efficacy analysis set is used for all analyses of the secondary parameters.

The semiquantitative SARS-CoV-2 serum functional antibody titer (percent inhibition) is summarized by arithmetic mean, standard deviation, minimum, median and maximum by visit. A boxplot graph will be presented.

The SARS-CoV-2 serum functional antibody titer is summarized by geometric mean, geometric coefficient of variation (CV) and 95% confidence intervals for the (geometric) mean. The Visits Screening, Visit 1/Week 1, Visit 2 /Month 1 and Visit3 /Month 6 are displayed separately in this summary table and a boxplot graph with logarithmic y-axis (log base 10).

The same summary table and boxplot will be provided for the following secondary parameters:

- a) Qualitative and quantitative result of IFNg towards SARS-CoV-2 and towards coronaviridae
- b) Qualitative and quantitative result of IL-2 towards SARS-CoV-2 and towards coronaviridae
- c) Combined response in qualitative INFg or IL-s towards SARS-CoV-2 and towards coronaviridae, i. e. reactive to INFg or IL-2 or to both.
- d) Cell viability, CD3 lymphocytes, CD4 and CD8 cells, percentage of CD4+ and CD8+ cell in peripheral blood mononuclear cells

The percent inhibition values for INFg at screening will be displayed for the subset of patients who are reactive at Week 1 versus non-reactive. The same analysis is provided for IL-2.

All other laboratory data (e. g. number of basal/background spots, spots, quality, comments, mutations) are listed only.

The MS activity is measured by relapses. The crude annual relapse rate until end of study and underlying sums (of relapses and patient-years) will be presented.

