## **4 Change to protocol specified analyses**

The definition for the Efficacy analysis Set was adapted to avoid that non-missing secondary endpoints would be excluded from the efficacy analysis set. For the rate of seroconversion (primary parameter) the patients with missing data are already excluded from the denominator.

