## 5.4 Rule of exclusion criteria of analysis sets

Deviation ID	Description of Deviation	Exclusion in Analyses
I01	Incl. crit. no. 1 (IFC) violated	Excluded from all analysis Sets
O05	Primary parameter (SARS-2-CoV-2 antibodies at Week 1) is missing	Excluded from denominator to calculate the rate of seroconversion

Table 2 Subject Classification

Analysis Set	PD ID that cause subjects to be excluded	Non-PD criteria that cause subjects to be excluded
all	NA	Not having informed consent;
SAF/Efficacy Analysis Set	NA	Not having any study treatment
Efficacy Analysis Set(s)	NA	Vaccination 1 not done or Vaccination not done with mRNA or Different vaccines at first and 2 nd vaccination or Positive neutralizing SARS-Cov-2 antibodies at screening

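### SAP 2.2 still makes a valid Week-1 antibody result the entry ticket to all secondary efficacy analyses, although SAP 4 and rule O05 were meant to drop that condition

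*SAP*

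**What the plan says.** SAP 2.2 defines a single efficacy set: the "efficacy analysis set will include all participants who have a valid primary endpoint", which it explains as the functional antibody determination at Week 1, plus anyone who missed the second dose. The footnote to that sentence says the second route is not applicable, "because all patients received their second dose of study vaccine".

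SAP 2.7.1 then states: "The efficacy analysis set is used for all analyses of the secondary parameters". Those parameters include antibody levels, IFN-gamma and IL-2 responses, and cell counts. The relapse rate is described in the same section.

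SAP 4 reports that the definition was "adapted to avoid that non-missing secondary endpoints would be excluded from the efficacy analysis set", and gives the reason that, for the seroconversion rate, "the patients with missing data are already excluded from the denominator". In SAP 5.4, deviation O05 (Week-1 antibody result missing) has the consequence "Excluded from denominator to calculate the rate of seroconversion". Table 2 of SAP 5.4 lists what removes a patient from the efficacy set, and a missing Week-1 result is not on the list.

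Protocol 12.1 has a separate efficacy set for each time point, based on a valid antibody result at that time point. It adds: "Patients completing vaccination but fail to provide a blood sample at one week after the second vaccination will be excluded from the study and analysis". Protocol 9.1.1 likewise says that patients who complete vaccination but "do not come to the center for the blood draw one week later (6-10 days after second vaccination) will be excluded from the study". Protocol 8, in contrast, says a missed visit should not by itself end participation, and allows repeat sampling when a sample is lost or cannot be used.

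**The concern.** SAP 2.2 and 2.7.1 put a patient without a valid Week-1 result outside every secondary efficacy analysis. SAP 4 and SAP 5.4 keep the same patient in the set and take the patient out of one denominator only. A programmer cannot follow both.

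The stake is which patients enter the Month-1 and Month-6 antibody, T-cell, cell-count and relapse summaries, in cohorts planned at about 20. If SAP 2.2 is followed, valid later data are left out, against the purpose stated in SAP 4. Baseline tables are also planned on the efficacy set, so their denominators depend on the same choice.

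**Working it through.** The point turns on definitions, so the first step is to follow three kinds of patient through the texts. All received both doses.

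| Patient | Protocol 12.1 (and 9.1.1) | SAP 2.2 with 2.7.1 | SAP 4 with SAP 5.4 |
|---|---|---|---|
| A. Week-1 sample given but invalid; valid antibody results at Months 1 and 6 | In the Month-1 and Month-6 sets | Out of all secondary analyses | In the set; not in the Week-1 rate |
| B. Week-1 draw missed; later data available | Out of study and analysis | Out of all secondary analyses | In the set; not in the Week-1 rate |
| C. Valid Week-1 result; T-cell data at Month 6 but no Month-6 antibody result | Out of the Month-6 set | In | In |

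- Patient C shows that SAP 2.2 delivers part of the declared change.
- Patients A and B show that it does not deliver the rest. For A it is stricter than the protocol set that it replaced.
- O05 would have no work to do if a patient without a Week-1 result were already outside the set. In the same table, I01 says explicitly that the patient leaves all analysis sets; O05 does not.

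Second, the size. The documents do not say how many patients lack a valid Week-1 result, so the count m per cohort is an assumption.

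- Planning figures (SAP 3): 22 enrolled per arm with 10% drop-out, 22 × 0.9 = 19.8, i.e. 20 evaluable.
- Assumed range: m = 0 to 2 of 22 per cohort (2/22 = 9%), or 0 to 6 of 66 overall. Two is an upper planning figure, because drop-out covers all reasons and the patient must also have later data.
- Week-1 seroconversion denominator: 22 − m under either reading, so the primary rate does not change.
- Month-1 or Month-6 summaries, taking the planned 20 evaluable as n under SAP 2.2: 20 under SAP 2.2, and 20, 21 or 22 under SAP 4 and O05 if none, one or two patients are affected.

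SAP 2.7.1 reports a 95% confidence interval for the geometric mean titer. On the log scale its half-width, in units of the SD, is t(0.975, n − 1)/√n:

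- n = 20: 2.0930/4.4721 = 0.4680
- n = 21: 2.0860/4.5826 = 0.4552
- n = 22: 2.0796/4.6904 = 0.4434

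Ratios at equal SD, taken before rounding: 20 against 21 gives 1.028, and 20 against 22 gives 1.056. The interval under SAP 2.2 is therefore wider by 0% (none affected), 2.8% (one) or 5.6% (two).

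**The case against.** SAP 4 can be read differently. The protocol's per-time-point sets lose patient C. One set anchored at Week 1 keeps that patient, which fits the stated purpose, and SAP 5.3.1 derives seroconversion at all three visits, so the remark about the denominator may refer to Months 1 and 6. On that reading O05 is merely redundant. It also speaks of a missing result, whereas SAP 2.2 speaks of a valid one. SAP 2.5.1 and 2.5.3, and protocol 2.1 and 12.3.3, exclude patients without a valid determination from the efficacy analysis. The protocol removes patients who miss the draw from the study altogether.

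Part of this stands. SAP 2.2 does carry out some of the change, and SAP 4 alone would not settle the matter. But this reading leaves O05 without effect and does not explain why Table 2 omits a Week-1 requirement. It also makes a change meant to retain data exclude patient A, whom the protocol would keep at Months 1 and 6. The passages in SAP 2.5 and in protocol 2.1 and 12.3.3 concern the primary estimand and do not govern the secondary parameters. The protocol exclusion covers a missed draw and not an invalid sample.

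The objection on size is also fair. Drop-outs usually have no later data, and if both planned drop-outs leave none, n is 20 under either reading and the difference is 0%. Repeat sampling under protocol 8 shrinks the group further. A set without a Week-1 requirement could also include patients with no result after vaccination, so the baseline tables must state which patients they describe.

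**Conclusion.** The concern holds. SAP 2.2, applied through 2.7.1, contradicts SAP 4 and SAP 5.4 and defeats the purpose that the SAP states for its own change. This rests on the current text of those sections; the SAP's document history only confirms the intent.

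The effect is limited. The Week-1 seroconversion rate is untouched, and what can change are descriptive secondary summaries and baseline tables on the efficacy set. The figure of 0 to 5.6% on interval width assumes 0 to 2 affected patients per cohort, equal SD on the log scale and the planned cohort size. The true number may be zero, in which case the two definitions give the same results. It should be fixed because it is a stated rule that contradicts the plan, and correcting it costs little.

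**What to change.** Rewrite SAP 2.2 so that the efficacy set is all participants not excluded by the criteria already in SAP 5.4: consent given, study treatment received, first vaccination done, mRNA vaccine used, same vaccine at both doses, and neutralizing antibodies negative at screening. Require no Week-1 result and add no new data-availability criterion. Then state that:

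- the seroconversion denominator at each visit is the patients with a valid antibody result at that visit, plus any without a second dose counted as non-responders;
- O05 applies to the Week-1 rate;
- all other secondary parameters use the data available at each visit.

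Clarifications to make at the same time:

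- SAP 2.5.1 and 2.5.3: say that the exclusions refer to the seroconversion rate.
- SAP 2.3 and 2.5.2: align the term for the efficacy set at Week 1 with the new definition, so that it is clear which patients the baseline tables describe.
- SAP 2.2: Week 1 is labelled Visit 2 there and Visit 1 elsewhere in the SAP; correct the label to Visit 1.
- SAP 4: state that this departs from the last sentence of protocol 12.1. Protocol 9.1.1 and 12.1, which exclude patients who miss the Week-1 sample, must be reconciled with it and with protocol 8.

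The cost is SAP wording in 2.2, 4 and 5.4, short clarifications in 2.3 and 2.5.1 to 2.5.3, one derivation flag, and a reconciling note for the protocol. No new data, visits or patients are needed.
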